Sponsor's Representative	[name] Admin Building, Level 2 Administration building Gartnavel Royal Hospital [name] Glasgow [contact] Email: [contact]
Sponsor	NHS Greater Glasgow and Clyde
Funder(s)	XXXXXXX
Key Protocol Contributors	[name] [name], Urology Research Fellow, Glasgow [name], Consultant Urologist, Glasgow [name], Statistician, Glasgow [name], Consultant Transplant Surgeons, Glasgow

SCIENTIFIC SUMMARY

Research questions:

1. What is prevalence and distribution of lower urinary tract symptoms (LUTS) in the renal transplant population?
2. Is there an association between pre-transplant LUTS scores and urological adverse outcomes following transplantation?

Background:

Urological consultation is an essential step in the pre-operative workup for patients before placing them on a waiting list for a renal transplant. The aim of this workup is to diagnose, treat and optimize any pre-existing urological pathology to maximize post-transplant graft function. Pre-existing lower urinary tract symptoms (LUTS) are common in patients with end stage renal disease (ESRD). Similarly, post-transplant urinary tract infection (UTI) is the most encountered complication. The European Association of Urology (EAU) recommends comprehensive lower urinary tract evaluation of patients prior to renal transplant. However the evidence on which these recommendations are based is limited and there is no standardized pathway followed across centers globally.

Aims and Objectives:

1. Primary objectives:

- a. To understand the distribution of LUTS score in patients undergoing renal transplantation
- b. To describe the distribution of LUTS scores across adverse outcomes post-transplant

2. Secondary objectives:

- To determine if there is a difference in distribution of LUTS scores between male and female patients
- To assess whether the presence of moderate to severe LUTS predict the occurrence of post-transplant significant urological complications in the 6 weeks and 12 months following transplantation.
- To evaluate whether the presence of moderate-severe LUTS can predict graft outcomes in the 12 months following transplantation
- To determine if duration of time on the transplant waiting-list and/ or RRT vintage and/or anuria predict objective change in LUTS or adverse urological outcomes post-transplant

- To determine if pre-existing urological conditions increase the likelihood of major urological complication following transplant
- To compare transient and persisting change in graft renal function over 12 months between patients with and without pre-transplant.
- To determine whether changing the peri-operative work-up pathway to evaluate pre-operative LUTS, will reduce the likelihood of urological complications in the year following transplant
- To inform sample size calculation and end points of a future larger intervention randomized trial

Methods:

A prospective single center longitudinal feasibility study to evaluate LUTS in patients at the time of waitlisting, day of transplant, 6 weeks and 1 year post transplant and evaluate the impact on post-operative urological complications will be undertaken.

The study will be conducted in two parts:

1. Evaluation of patients beginning on day of transplant, prospectively at 6 weeks and 1 year
2. Evaluation of patients at time of waitlisting, prospectively 1-year post-waitlisting (if not yet transplanted), on day of transplant and at 6 weeks and 1-year post-transplant

We aim to approach all patients at the time of transplant and at the time of transplant wait-listing to be consented.

All patients who consent will undergo baseline assessment of LUTS (clinical history, validated questionnaires, Uroflowmetry and Post Void Residual measurement). For patients who do not produce enough urine to provide a sample for Uroflowmetry (130mls), urinary catheter or flexible cystoscope will be used to fill the bladder and perform the study.

Where clinically indicated, patients will undergo invasive urodynamic studies.

The use of invasive urodynamics (filling cystometry) will be reserved for following patients:

1. Diagnostic uncertainty despite the clinical history, questionnaires and non-invasive urodynamics.
2. Failure to provide a diagnostic uroflowmetry on 2 occasions despite using cystoscopy to fill the bladder.

3. If initial workup reveals a possibility of neurogenic lower urinary tract dysfunction (NLUT)

Repeat assessment of symptomatology, urological complications and graft function will be assessed at 6 week and 1 year post-transplant.

LUTS will primarily assessed using IPSS for male participants and ICIQ-FLUTS for female participants (see below), supplemented by post-void residual volume and urine flow studies.

The “urological complication” will be a composite any of the following occurring within the first 12 months following transplantation:

1. Urinary retention defined as high post-void residual volumes initiating need for indwelling catheter (IDC)/ clean intermittent catheterization (CISC) within the first 12 months of transplantation. (This will include patients who fail trial of void post-surgery).
2. Recurrent culture-proven urinary tract infections (≥ 3 in the first 12 months post-transplant)
3. Ureteric leak or suspected ureteric leak requiring surgical or radiological intervention
4. Deterioration in renal function (eGFR, Creatinine) due to post-renal causes:
 - Transient decline in renal function ($>20\%$ from nadir creatinine)
 - Persistent decline in renal function ($>10\%$ from nadir creatinine)
5. Sepsis of urinary source requiring hospital admission (including graft pyelonephritis)
6. Any patient undergoing any surgical or radiological intervention for a urological complication (excluding routine stent removal post-transplant) within the first 12 months of transplantation
7. Graft loss as a result to urological complications within the first year of transplantation

Secondary outcomes will include:

1. Evidence of urological complications in the 6 weeks following transplantation.
2. Evaluation of whether the presence of moderate-severe LUTS can predict graft outcomes in the 12 months following transplantation
3. Determination if the duration of time on the transplant waiting-list and/ or RRT vintage and/or anuria predict objective change in LUTS or adverse urological outcomes post-transplant

4. Whether or not pre-existing urological conditions increase the likelihood of major urological complication following transplant
5. Compare patients undergoing this work-up regimen with an age/ sex matched historical cohort to determine if there is any difference in risk of post-operative urological complications with a focused pre-operative screening regimen.
6. Determination of whether changing the peri-operative work-up pathway to evaluate pre-operative LUTS, will reduce the likelihood of urological complications in the year following transplant

Timeline for delivery:

Recruitment will commence in January 2026 and is anticipated to continue for 2 years. Follow-up will cease when all patients recruited are > 1 year post-transplant; have been removed from the transplant waiting-list or will have died.

Anticipated impact and dissemination:

It is anticipated that results will directly impact patient care and help stratify patients before transplantation. This will allow us to implement bladder optimizing protocols to maximize post-transplant graft function.

The results will be presented at international platforms and will be published in high-impact medical journals, which will help fill a lacuna in the literature. This may pave way for a future multicenter interventional study.

ABBREVIATIONS

PLAIN ENGLISH SUMMARY

Many patients with kidney failure need a kidney transplant. Some of these patients will have problems relating to the storage or passage of urine. In many cases this is unrecognized before transplant, especially if the patient no longer passes urine. This can lead to problems after the transplant, resulting in infections, complications and poor kidney function.

There are very few studies which have looked at how issues with the patient's urinary tract and bladder affect the outcome of kidney transplant. However, it's well-recognized amongst kidney transplant surgeons to be a significant problem. This study aims to determine the number of patients who have undiagnosed waterworks issues before transplant and investigate if these issues make it more likely for the patient to have urinary tract infections, poor kidney transplant function or other complications in the year following transplant.

We will approach everyone having a kidney transplant in Glasgow within a two-year period: both when they join the transplant waiting list and when they receive a transplant. We will follow patients up at 6 weeks and 1 year after transplant, taking measures of bladder function from history, questionnaires and simple studies of urine flow/ bladder function. We hope to recruit 100 patients over in each group over a two year period.

Currently there is no standardized suggested work-up of the bladder and urinary tract prior to kidney transplant. Different transplant centers do different things and there is no agreed best approach. We hope that results from this study might better inform how and why a patient's lower urinary tract should be assessed before transplant. In doing so, we hope to reduce complications and improve outcomes for after transplant. If we find that there are identifiable problems pre-transplant that predict complications after transplant, we'd hope that the results of this study could inform a larger study in the future where we could intervene on these issues pre-transplant to see if it prevents complications in the future. However, at the moment, we don't know what to measure or how best to intervene. It's hoped that this study would help us better understand these issues

FUNDING:

ROLE OF STUDY SPONSOR

The trial is sponsored by NHS Greater Glasgow and Clyde.

The sponsor is responsible for ensuring that proper arrangements are in place to initiate, manage, monitor and finance the study in line with the Research Governance Framework and Good Clinical Practice.

Specifically, the sponsor is responsible for ensuring that:

- the trial is appropriately assessed and resourced
- the trial is conducted to the required standards and conforms with regulatory requirements
- There is adequate provision for compensation and indemnity in the event of harm to research participants.

Some of these responsibilities will be delegated to the Chief Investigator.

The sponsor will maintain oversight for all aspects of the trial and will be responsible for monitoring trial progress.

ROLES AND RESPONSIBILITIES OF STUDY MANAGEMENT COMMITTEES/GROUPS & INDIVIDUALS

Study Steering Groups

[figure not shown]
An oversight committee which includes representatives of the research team, an interested independent clinician and a patient representative will be assembled to oversee the project; ensure milestones are reached and to identify emerging findings. The study steering group will meet online every 12-24 weeks and minuted outcomes will be described

PROTOCOL CONTRIBUTORS

[figure not shown]
The protocol was written by the [name] [name] with oversight from the Chief Investigator [name] and [name] and input from the coinvestigators ([name] and [name]). The project sponsor is NHS Greater Glasgow and Clyde.

TRIAL FLOW CHART

Phase 1: Patients recruited at time of kidney transplant

Phase 2: Patients recruited at time of waitlisting

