6. PARTICIPANT ELIGIBILITY CRITERIA

Inclusion criteria

All adult patients (≥ 18 years old) scheduled to undergo first time renal transplantation (both deceased and living donor candidates).

Exclusion criteria

- Unable or unwilling to provide consent
- Patients undergoing re-transplant (to avoid confounding because of previous interventions)
- Patients undergoing simultaneous urological reconstructive procedures
- Patients with previously reconstructed bladders (includes Augmentation cystoplasty, ileal conduit, neobladder etc.)
- Significant cognitive impairment which would limit their capacity to accurately report symptoms

In line with NIHR guidance on equality, diversity and inclusion all people regardless of gender, sexual orientation, pregnancy, ethnicity, religion and socioeconomic status will be offered the same opportunity to participate. Hospital translators will be used where appropriate to obtain consent and the HR-QoL tools employed are available in a large variety of languages. Where it may not be possible to provide a translated HR-QoL tool, this will not serve as a contraindication to participation should the patient wish to, rather this secondary outcome measure will be omitted from data collection.

Both for equity and for scientific integrity, it's important that roughly equal numbers of men and women complete the study (as men will complete an IPSS and woman a ICIQ-FLUTS). Recruitment will be reviewed after 70 patients and patients targeted based on gender to ensure a fairly equal number of male and female participants.

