Transplant specific factors: Donor age, gender, any pre-existing/ known urological history in donor or anatomic irregularity with kidney e.g. duplex collecting system, dual transplant, horseshoe kidney, renal stones, renal cysts etc.), DBD/ DCD/ live donor, CIT, cRF, immunosuppressive regimen and induction agent, other relevant aspects of post-transplant course e.g. DGF, primary non-function, biopsy-proven rejection and treatment for same; documented operative complications with initial surgery

Bladder diary

We will be using the form prescribed by ICIQ (<https://iciq.net/iciq-bladder-diary>)

IPSS/ ICIQ-FLUTS

LUTS will be assessed by taking a complete urological history and using validated, gender appropriate questionnaires:

- Males: We will use the International Prostate Symptoms score (IPSS). Moderate to severe LUTS will be defined if the score is above 7¹⁵.
- Females: We will use the International Consultation on Incontinence Questionnaire – Female Lower Urinary Tract Symptoms (ICIQ-FLUTS). It does not have a total score, but instead measures the severity of following subscales separately:
 - Incontinence 0-20
 - Voiding 0-12
 - Filling 0-16

Whilst there is no official cutoff for severity for ICIQ-FLUTS, we aim to use the following cutoffs based on the published evidence¹⁷⁻¹⁹:

- Mild: total score 0–11
- Moderate: 12–23
- Severe: 24+

This stratification will ensure an accurate gender-specific assessment of baseline urinary symptoms and will allow the results to be meaningful, across subgroups having external validity.

Post-void residual bladder volume

This is a routine bedside test which uses a non-invasive ultrasound “bladder scanner” to measure how much urine is left in the bladder after a patient has urinated. The patient is asked to go to the bathroom to void urine and the urine void is captured and measured. Immediately following the urine void, a bladder scan of the residual (remaining) fluid levels within the bladder is made.

As some renal patients have been on dialysis for many years, there is a chance that a small number are anuric or do not make sufficient urine to make this scan reliable. In these situations (where the patient is able to pass less than 130ml at a single void), a cystoscopy (telescope test) will be performed to fill the bladder with fluid artificially and then the patient asked to void and the test repeated to ensure that an accurate result is obtained.

Uroflowmetry

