We aim to describe both IPSS (male) and ICIQ-FLUTS (female) in combination and separately. We would therefore hope to achieve roughly similar numbers of males and females recruited into the study. We'd therefore aim to evaluate recruitment after 70 patients and if gender distribution were unequal, target as required.

We anticipate it should be large enough to allow for 5-10% death rate (as would be standard in the transplant population). We do not anticipate that patients will be lost to follow-up as they all come back to regular post-transplant clinics but assuming 5-10% withdraw or have incomplete data sets. This is primarily an exploratory study. Little data exists about the prevalence of LUTS in renal/kidney transplant recipients. It is anticipated that the results of this study will inform sample size calculations for future interventional studies.

Data collection

All data will be collected within a password protected Microsoft Excel spreadsheet stored on an NHS-password protected computer. No patient identifiable information will be included within that spreadsheet only unique patient identifiers.

Data analysis

Data analysis will be exploratory with the primary aims of describing the distribution of LUTS scores for males and females and determining the prevalence of urological complications. These factors could inform sample size calculation, determine the correct primary endpoint for a future interventional study.

If appropriate, we may/ may not attempt to:

- Investigate the relationship between LUTS severity and urological complications
- Describe any change in LUTS whilst on the transplant waiting list/ post-transplant
- Establish a risk model for urological complications post-transplant.

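### The male-female comparison of LUTS scores cannot be answered, because men complete only the IPSS and women only the ICIQ-FLUTS

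*Protocol*

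**What the plan says.** The Scientific Summary lists among its secondary objectives "To determine if there is a difference in distribution of LUTS scores between male and female patients". Its Methods paragraph assigns the instruments: "LUTS will primarily assessed using IPSS for male participants and ICIQ-FLUTS for female participants". Section 3 repeats this, and section 6 gives it as the reason for wanting similar numbers of each sex ("as men will complete an IPSS and woman a ICIQ-FLUTS"). No participant completes both questionnaires, and no common questionnaire, cross-walk or standardisation is described.

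Section 8, under Sample size, adds: "We aim to describe both IPSS (male) and ICIQ-FLUTS (female) in combination and separately". It does not say how the two would be combined.

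Section 7 sets the severity grades. For men, moderate to severe means an IPSS above 7. Of the ICIQ-FLUTS it says "It does not have a total score, but instead measures the severity of following subscales separately", listing subscales of 0-20, 0-12 and 0-16. It then grades a total (0-11, 12-23, 24 and over), introduced by "Whilst there is no official cutoff for severity for ICIQ-FLUTS, we aim to use the following cutoffs based on the published evidence".

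Uroflowmetry, post-void residual and a bladder diary are scheduled for both sexes at every assessment (section 7, Study visits). Section 3 treats flow and residual volume as supplements to the questionnaires.

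**The concern.** A comparison of score distributions between men and women needs a score that means the same thing in both. Here every male score comes from one tool and every female score from another, with different items and different thresholds. Whatever difference appears is the sum of a sex effect and an instrument effect, and the data hold nothing to split that sum.

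The study is meant to inform endpoints and sample size for a later interventional trial. A scale artefact reported as a sex difference would carry into that design. The same applies to moderate-severe LUTS, which the Scientific Summary uses as a predictor of urological complications and of graft outcome. If the two thresholds are not equivalent, a predictor pooled over both sexes partly records which questionnaire was filled in.

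**Working it through.** **1. The plan's own figure.** Section 8 expects at least 40 men and 40 women with complete data from 100 recruits per part. With 10% deaths and 10% withdrawn or incomplete, 100 × (1 − 0.10 − 0.10) = 80, or 40 per sex. Taken multiplicatively, 100 × 0.9 × 0.9 = 81, or 40.5 per sex. The figure reproduces. The protocol states no alpha, power, effect size or SD.

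**2. Identifiability.** Take 80 people and three columns: intercept, sex (0 for 40 men, 1 for 40 women) and instrument (0 for IPSS, 1 for ICIQ-FLUTS). The second and third columns are identical, so the matrix has rank 2, not 3. This does not depend on the number of patients or on the sex balance.

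**3. Do the severity grades bridge the tools?** The female total is 20 + 12 + 16 = 48, so the moderate grade starts at 12/48 = 25% of the summed range. The protocol gives no IPSS range, so not even this crude check can be made for men. The female grades are applied to a total that the same section says the tool does not have. Equivalence of the two thresholds is assumed, not shown.

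**4. What an artefact could look like (illustration only).** Assume no true sex difference, 40 per sex, two-sided alpha 0.05 and an instrument offset of d SD. None of these except the 40 comes from the protocol. The chance of a significant result is Φ(d/√(2/40) − 1.96) + Φ(−d/√(2/40) − 1.96), with √(2/40) = 0.224:

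| Assumed offset d | Probability |
|---|---|
| 0.2 | 0.15 |
| 0.3 | 0.27 |
| 0.5 | 0.61 |
| 0.8 | 0.95 |

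For the severity grade, suppose that non-equivalent cutoffs alone gave the proportions below. The chance is Φ([|p1 − p2| − 1.96·√(2p̄(1 − p̄)/40)] / √([p1(1 − p1) + p2(1 − p2)]/40)), where p̄ is the mean of p1 and p2:

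| Assumed proportions moderate-severe | Probability |
|---|---|
| 30% vs 40% | 0.15 |
| 30% vs 50% | 0.45 |
| 30% vs 60% | 0.78 |

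**5. What a shared measure would give.** On a measure taken identically in both sexes, with 40 each, the 95% confidence interval for the sex difference has half-width 1.96 × 0.224 = 0.44 SD. The difference detectable with 80% power is (1.96 + 0.84) × 0.224 = 0.63 SD. If both sexes also completed one common questionnaire, the matrix with intercept, sex and two instrument contrasts (160 scores from 80 people) has rank 4 of 4. The sex effect is then estimable, assuming additive effects.

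**The case against.** The strongest reply concerns scope. The male-female objective stands only in the Scientific Summary. It is absent from the section 3 objectives, from the endpoint table and from the Data analysis paragraph of section 8. That paragraph is exploratory, speaks of describing scores for males and females, and specifies no test between them. Sex-specific questionnaires are a reasonable choice, and shared measures are already collected. All of this stands. It lowers the severity and makes the repair cheap, but it does not make the objective answerable. A later analysis plan cannot supply the missing information, because the instruments are fixed here. The probabilities in the working illustrate the mechanism. They do not estimate harm in this study.

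Three stronger readings are tempting, and the protocol does not support them.

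- A reader might infer that primary objective (a) is uninterpretable. It is not, because the distribution of each score within its own sex is sound. Nor must the combined description mean pooling raw scores: it could mean counting patients by severity grade. That count has a unit, but its meaning still depends on thresholds not shown to be equivalent.
- A reader might try to state the artefact in score points by comparing the two scale ranges. The protocol gives no IPSS range, and equal fractions of two ranges need not mean equal severity.
- A reader might add that sex-targeted recruitment distorts pooled results ("Recruitment will be reviewed after 70 patients and patients targeted based on gender to ensure a fairly equal number of male and female participants"). Section 8 makes targeting conditional on imbalance, the protocol gives no expected sex mix, and it does not say which 70 patients are meant. Any size for this effect would rest on assumptions alone.

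**Conclusion.** The point holds at moderate severity. The objective of comparing LUTS score distributions between men and women cannot be met with the planned questionnaires, because sex and instrument coincide exactly. This follows from the design and needs no numerical assumption. The severity grades do not rescue it: on section 7's own account the female grade rests on a tool without a total score or an official cutoff.

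The consequence extends to the combined description in section 8 and to any analysis that uses moderate-severe LUTS as a predictor over both sexes without stratifying. It does not extend to descriptions within each sex. The size of a spurious difference cannot be fixed from the protocol. The 0.15 to 0.95 range applies only under the assumed offsets, alpha and significance test.

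**What to change.** - **Objective.** Reword the Scientific Summary objective so that the sexes are compared only on measures taken the same way in both: Qmax, post-void residual and bladder-diary variables. Then add it to section 3, or remove it from the summary, so that the two lists agree.
- **Description.** Report IPSS and ICIQ-FLUTS by sex, and delete the combined description of the scores from section 8. If a combined count by severity grade is kept, state both thresholds, say that they are not known to be equivalent, and show the figures for each sex beside it.
- **Association analyses.** Stratify LUTS-complication and LUTS-graft analyses by sex, or use scores standardised within sex.

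This changes wording only and needs no new data. The cost is that no questionnaire-based sex comparison is reported. The shared flow and residual measures describe bladder function, which is not the same as symptom burden.

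If a comparison of symptom scores is wanted, both sexes would have to complete one common questionnaire. That adds burden and must be settled before baseline assessments begin, because missed baselines cannot be recovered.

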3. OBJECTIVE AND OUTCOME MEASURES/ ENDPOINTS

Primary objectives

The primary objectives are twofold:

- a. To understand the distribution of LUTS score in patients undergoing renal transplantation
- b. To describe the distribution of LUTS scores across adverse outcomes post-transplant

Secondary objectives

- Evidence of urological complications in the 6 weeks following transplantation.
- Evaluation of whether the presence of LUTS can predict graft outcomes in the 12 months following transplantation
- Whether or not pre-existing urological conditions increase the likelihood of major urological complication following transplant
- Compare patients undergoing this work-up regimen with an age/ sex matched historical cohort to determine if there is any difference in risk of post-operative urological complications with a focused pre-operative screening regimen.
- Determination of whether changing the peri-operative work-up pathway to evaluate pre-operative LUTS, will reduce the likelihood of urological complications in the year following transplant
- To assess the change in LUTS and QOL by validated tools at 6 weeks and 1 year post RT after re-establishment of diuresis.
- To assess whether duration of time on the waiting list/ presence of anuria impacts on primary outcomes and change in severity of LUTS/ QoL. Inform future end points, sample size, trial design etc. of a future interventional study
- Determination if the duration of time on the transplant waiting-list and/ or RRT vintage and/or anuria predict objective change in LUTS or adverse urological outcomes post-transplant

Primary outcome measures

LUTS will primarily be assessed using IPSS for male participants and ICIQ-FLUTS for female participants (see below), supplemented by post-void residual volume and urine flow studies.

“Urological complication” will be considered to be a composite any of the following occurring within the first 12 months following transplantation:

1. Urinary retention defined as high post-void residual volumes initiating need for indwelling catheter/ clean intermittent catheterization within the first 12 months of transplantation. (This will include patients who fail trial of void post-surgery).
2. Recurrent culture-proven urinary tract infections (≥ 2 in the first 6 months/ ≥ 3 in the first 12 months post-transplant)
3. Ureteric leak or suspected ureteric leak.
4. Deterioration in renal function (eGFR, Creatinine) due to post-renal causes:

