 - Transient decline in renal function ($>20\%$ from nadir creatinine)
 - Persistent decline in renal function ($>10\%$ from nadir creatinine)
5. Sepsis of urinary source requiring hospital admission (including graft pyelonephritis)
6. Any patient undergoing any surgical or radiological intervention for a urological complication (excluding routine stent removal post-transplant) within the first 12 months of transplantation
7. Graft loss as a result to urological complications within the first year of transplantation

Secondary outcome measures

- Renal function at 12 months (eGFR, creatinine) and its association with presence and severity of pre-transplant LUTS
- Change in IPSS/ ICIQ-FLUTS scoring from baseline to 6 weeks and 1 year post RT (including QoL scores)

Table of endpoints/ outcomes

Objectives	Outcome Measures	Timepoints
Primary Objective:		
To determine the prevalence of distribution of pre-transplant LUTS	LUTS at baseline as assessed by IPSS/ ICIQ-FLUTS, flow studies and post-void residual urine volumes	Baseline
To determine the distribution of LUTS scores across adverse urological complications post-transplant	Incidence of urological complications (retention, recurrent UTIs, ureteric obstruction, need for CIC, graft pyelonephritis etc as above)	6 weeks and 12 months post-transplant
Secondary Objectives:		
To assess change in LUTS over time (includes QoL)	IPSS/ ICIQ total score and QoL sub-score, post-void residual volumes, Qmax	Baseline, 6 weeks, 12 months
To describe urological complications in patients with and without LUTS	Frequency and type of complications	6 weeks and 12 months
To correlate pre-transplant LUTS with graft function	Renal function measures (eGFR, creatinine)	6 weeks, 12 months
Impact of waiting times on outcomes	IPSS/ ICIQ total score and QoL sub-score	12 months post wait listing

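### Two predictive secondary objectives name a yes/no LUTS group although the research question concerns the score; making the score the main predictor is a cheap improvement

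*Protocol*

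**What the plan says.** The Scientific Summary (Secondary objectives) sets two predictive objectives on a two-group exposure. For complications: "To assess whether the presence of moderate to severe LUTS predict the occurrence of post-transplant significant urological complications", at 6 weeks and 12 months. For the graft: "To evaluate whether the presence of moderate-severe LUTS can predict graft outcomes in the 12 months following transplantation". The summary's list of secondary outcomes repeats the graft objective: "Evaluation of whether the presence of moderate-severe LUTS can predict graft outcomes in the 12 months following transplantation".

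Section 7 (IPSS/ ICIQ-FLUTS) supplies the cuts. For men, moderate to severe means IPSS above 7. For women the protocol says: "Whilst there is no official cutoff for severity for ICIQ-FLUTS, we aim to use the following cutoffs". It then sets mild at 0–11, moderate at 12–23 and severe at 24 or more, all on a total score. The same section says that this instrument has no total score, only three subscales.

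Elsewhere the exposure is the score or its severity:

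- Research question 2: "Is there an association between pre-transplant LUTS scores and urological adverse outcomes following transplantation".
- Primary objective b: "To describe the distribution of LUTS scores across adverse outcomes post-transplant".
- Section 3, secondary outcome measures: "Renal function at 12 months (eGFR, creatinine) and its association with presence and severity of pre-transplant LUTS".

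Section 3 also restates the graft objective without a severity threshold: "Evaluation of whether the presence of LUTS can predict graft outcomes in the 12 months following transplantation". Its endpoint table has a row comparing complications between patients with and without LUTS. Section 8 (Data analysis) lists the relation of LUTS severity to complications among analyses that may or may not be attempted, and names no model.

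**The concern.** The two objectives that use the language of prediction define the exposure more coarsely than the question they serve. A man scoring 8 is grouped with a man scoring 30 and separated from one scoring 7. The full score is already collected at every visit, so this information would be discarded at the analysis and not for want of data.

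The sample is small for this. Men and women complete different instruments, and the protocol's own minimum is 40 of each with complete data. Carried out as worded, the objectives could miss a real gradient of risk across the score. One of the study's stated uses is to inform the endpoints and sample size of a later trial, and a slope or effect per SD would serve that better than a contrast at one pre-set cut.

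**Working it through.** **1. The protocol's own figure.** Inputs from section 8: 100 recruited per part, roughly equal by sex (50 each), 5–10% deaths, 5–10% withdrawn or incomplete.

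- Worst case, multiplicative: 50 × 0.90 × 0.90 = 40.5 per sex.
- Worst case, additive: 50 × (1 − 0.20) = 40.0 per sex.
- Best case: 50 × 0.95 × 0.95 = 45.1 per sex.

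The stated minimum of 40 men and 40 women reproduces.

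**2. Information kept after one split.** Section 8 assumes a relatively normal score. For a normal score with a linear effect, if a share p lies above the cut and z is the matching normal quantile, the fraction of information kept is φ(z)² / [p(1 − p)]. The protocol gives no value for p (it reports little data in men and none in women), so p is an assumption and is shown as a range.

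| Share above cut, p | φ(z) | Kept | Lost | 40 patients are worth |
|---|---|---|---|---|
| 0.50 | 0.399 | 0.637 | 36% | 25.5 |
| 0.35 | 0.370 | 0.603 | 40% | 24.1 |
| 0.30 | 0.348 | 0.576 | 42% | 23.0 |
| 0.20 | 0.280 | 0.490 | 51% | 19.6 |
| 0.10 | 0.175 | 0.342 | 66% | 13.7 |

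Example, p = 0.30: 0.348² / (0.30 × 0.70) = 0.121 / 0.21 = 0.576. The median split is the best case, so 36% is the smallest possible loss under these assumptions.

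**3. What this does to power.** The protocol states no power, significance level or effect size, so these figures are illustrative. Assumed: odds ratio 2 per SD and two-sided 5%. From section 8: an event rate of 55%, the middle of its 50–60%. Score tests, 3,000 simulated studies per setting:

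| n | Score | Split, p = 0.50 | Split, p = 0.30 | Split, p = 0.20 |
|---|---|---|---|---|
| 40 (one sex) | about 51% | 35% | 31% | 26% |
| 80 (both sexes) | about 82% | 65% | 57% | 49% |

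When the 80 are analysed as 40 men and 40 women stratified by sex, with the same slope per SD in both, the score gives about 81%. The split gives 62% at p = 0.50 and just under 50% at p = 0.20.

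**4. If the score is not normal.** With a right-skewed (gamma) score and the same odds ratio, power at n = 40 is about 42% on the score against 29–33% on the split. At n = 80 it is about 75% against 55–61%. The gap narrows but remains.

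**5. Pooling.** A pooled split at n = 80 (49–65%) can match or beat a single-sex score analysis at n = 40 (about 51%). The gain from using the score is therefore secure only if the score analysis also combines the sexes.

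**The case against.** The strongest reply is that the protocol does use the score. Primary objective b describes scores across outcomes, and the renal-function outcome measure refers to severity as well as presence. Section 3 contains no complication objective worded on moderate to severe LUTS. This stands. A reader might infer that the study replaces the score with a yes/no group throughout, or that it will give a future trial no evidence on where a threshold should lie. The documents support neither inference, because score distributions by outcome are a primary objective and the full scores are kept.

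A reader might also infer that a yes/no test has been specified. It has not: section 8 makes the association analysis optional and fixes no model, and how a predictor enters a model is commonly left to an analysis plan, which is not at hand. The objectives nevertheless name the two-group exposure, so an analysis plan built on the score would depart from them.

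A common yes/no category also puts two different instruments on one footing and lets men and women be combined. That is a fair point against analysing IPSS and three ICIQ-FLUTS subscales separately in about 40 people each, which could cost more power than the split does. It does not count against a score standardised within sex, which also combines them.

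Finally, the study is exploratory and claims no power, and a clinical category is easy to communicate. That is a reason to keep the category as a summary, but not as the main predictor.

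**Conclusion.** The point holds as a cheap improvement and a correction of inconsistent wording. The two predictive secondary objectives use a coarser exposure than research question 2 and primary objective b. Followed literally, they would discard at least 36% of the information, and about 40–51% if 20–35% of patients exceed the cut.

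These figures rest on a roughly normal score, a linear effect on the outcome and an assumed share above the cut. A single figure such as 40% is therefore not a result of the protocol. If risk truly jumped at the chosen cut, the loss would not arise in this form. The power comparison rests further on an assumed odds ratio of 2 per SD and a 5% level. The sample of about 40 per sex in each part is the protocol's own minimum.

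**What to change.** Reword the complication and graft objectives in the Scientific Summary, the repeated graft item in its secondary outcomes, and the matching lines in section 3 (the graft objective and the with/without-LUTS row of the endpoint table), so that the pre-transplant score is the main predictor.

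To combine men and women, either standardise the score within sex or use a sex-stratified rank test or a sex-stratified logistic or linear model. Show results per instrument alongside. Keep the moderate-severe category as a supportive, descriptive summary.

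For women, first reconcile the section 7 statement that ICIQ-FLUTS has no total score with the cut-offs set on a total. Until that is settled, the female score to be standardised is undefined.

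The cost is a few lines of wording, with no new data or visits. The headline becomes less simple than yes/no groups, and the combined analysis assumes a similar slope per SD in both sexes, which the per-instrument results would help to check.
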